Although health promotion related to weight, diet, smoking, alcohol intake and physical activity is part of the usual rehabilitation in CSCI, a systematic approach, follow up and feedback is not provided. Assessment of metabolic profile, body composition and physical capacity is not part of the usual care. In the masterplan for patient care at CSCI, health promoting initiatives are described as "communication and conversation with a health promoting purpose with the patient on a daily basis". How the communication is carried out in practice, and whether some health care professionals have a particular responsibility or expertise related to certain aspects of health promotion eg. based on tests or assessments of health, is unclear and not described in detail. A well described and systematic approach related to health care promotion may ensure that all patients at CSCI receive information and knowledge related to health promotion and the risk of cardiovascular disease.

Sub projects

The project consists of a prospective national survey in collaboration with Spinal Cord Injury Centre of Western Denmark and an intervention at CSCI (see the timeline), which results in 4 sub projects

Sub project 1. Prospective representative national survey of Body Mass Index.

This study includes all patients with a new SCI hospitalized at CSCI or Spinal Cord Injury Center of Western Denmark during a period of 9 months whereby 100 patients are expected to participate. On the basis of usual rehabilitation today, data concerning BMI, level of functioning (SCIM III) and neurological status (ISNCSCI) are collected at admission and discharge. At CSCI BMI is collected every 6 weeks. Also the data for quality of life (QoL SCI), depression (PHQ-2), PA (LTPAQ-SCI) and self-assessed ability to be physically active (ESES) will be collected during this period and at follow up 6 months after discharge. A VO₂peak test at discharge is performed and in some patients measurements of accelerometry (AH) will be performed. Patients with a new SCI who are admitted for rehabilitation several months after the time of injury are also included in the prospective survey. Therefore the data for BMI at the time of injury is collected for all patients at admission to primary rehabilitation from both the patient journal and also by asking the patient about weight and height at the time of injury. Data from this subproject serves as a historic control in the Ph.D project.

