This study includes a subsample of 20 patients participating in subproject 1. The equipment used for monitoring amount and intensity of PA consists of sensors registering acceleration and heart rate and is placed on the thorax of the participant with two surface electrodes. The equipment has previously been used in wheelchair dependent people with SCI, although the reliability of the equipment has not previously been assessed [35]. The precision of the equipment is higher when calibrated individually to the participant using an exercise test [68]. In this project individual calibration will be made during the exercise test described in subproject 3, and continuous measurements of amount and intensity of PA will be made during a period of 24 hours. The test-retest is performed at discharge, separated by 48 hours or within maximum 5 days at the same time of the day.

Outcome measures

All outcome measures will be collected at admission, discharge and follow-up 6 months after discharge. At CSC data for BMI is also collected every 6th week during the hospitalization period.

Primary outcome

Oxygen uptake: Is measured as VO₂peak during a maximal exercise test and is gold standard for measuring aerobic capacity. For people with a SCI several test protocols have been used [36]. The test in this project is performed by using the integrated test protocol in the software of NuStep XR5 or SCI FIT Pro 1. Gradual increments in workload is added every minute depending on the level of lesion. The participant maintains a fixed cadence until predefined criteria for VO₂peak is reached after 8-12 minutes. If VO₂peak is not reached during this period the workload increases each minute until VO₂peak [36, 67]

Secondary outcomes

Objective physical activity: Is measured in a sub-sample in the historic control cohort and the participants in the intervention study with a multisensor device (Actiheart®) recording accelerations and heart rate. It is previously used for wheelchair users with a SCI and individual calibration is important to get the most accurate data [29].

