Neurological status: Is determined by the International Standards for Neurological Classification of Spinal Cord Injury (ISNCSCI) and is the most widely used classification in people with SCI [36, 37]. The classification tool involves a sensory and motor examination to determine the neurological level of the injury and whether the injury is complete or incomplete. The ISNCSCI defines neurological level as the most caudal level at which sensory and motor function are intact. The completeness of the injury is graded according to the ASIA Impairment Scale (AIS). AIS is used to determine the degree of motor and sensory function below the level of the SCI. A complete or incomplete injury is defined as absence or presence of sensory and motor function in the most caudal sacral segment. A = complete; B = sensory incomplete without motor function > 3 levels below the motor level of injury on both sides of the body; C = motor incomplete, with preserved motor function below the level of injury and where > 50% of the key muscles below the injury level have a degree < 3 by MMT; D = motor incomplete with preserved motor function below the level of injury and where > 50% of key muscles below the injury level have a degree > 3 by MMT; E = normal sensory and motor function in all segments. ISNCSCI Is already collected as part of the existing routines at CSCI.

Depression: Is measured by the Patient Health Questionnaire- 2 (PHQ-2) which is a generic outcome measure for measuring depression. In people with SCI a cut-off score of 3 is associated with a sensitivity of 83,3% and specificity of 95,7% [38]. PHQ-2 is already collected at admission as part of the existing routines at CSCI

Quality of Life: Is measured by the International SCI Quality of Life Basic Data Set (QoL SCI) which consists of three questions regarding satisfaction with life in general as well as physical and mental health. It is a valid outcome measure with good internal consistency [39] [40]. QoL SCI is already collected at discharge as part of the existing routines at CSCI.

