Data from the patient journals in Epic and the different outcome measures used, is stored in a web based database (Redcap) which is created by the regional Centre for IT, Medico and Telephony (CIMT), with limited access and ID- code, to which pseudo anonymized data is transferred directly,

or via an encrypted USB-stick. An identification list is stored in a locked cabinet at CSCI, local 3403.

Data is stored until December 31, 2027 after which paper material is shredded and data files are deleted.

Statistics

The intervention study and follow up is performed as a pragmatic study and includes, with a few exceptions, all newly injured patients with SCI admitted to primary highly specialized rehabilitation at CSCI. Patients will be included during a time period of 18 corresponding to approximately 40 – 60 patients. Due to the rareness of the morbidity a power calculation is not performed for the primary outcome prior to the intervention, but it is assumed that the total participant number in the intervention and in the historic control cohort, will be comparable to the existing scientific literature.

Numeric continuous data collected at admission, discharge and follow up is reported descriptively as mean and standard deviation together with 95% confidence intervals, or as median, upper and lower quartile as well as interquartile range. Changes over time is reported on the basis of paired t-test. In subproject 3 and 4 the reliability of the outcome measures is analyzed by paired t-test, Pearsons product moment correlation and coefficient of variation or Intraclass correlation coefficient between the test- retest sessions.

Participants, inclusion- and exclusion criteria

Inclusion criteria: All newly injured patients within the previous 12 months, with a SCI and admitted at CSCI are included, regardless of age, neurological level of lesion and completeness of the injury. In subproject 1 all newly injured people with SCI admitted at VCR are also included. Patients under the age of 18 will participate if informed consent is retrieved from their parents.

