Exclusion criteria: Insufficient skills in Danish language and reduced mental function that prevents reading and answering the questionnaires. For the VO₂peak test: Motor complete SCI (AIS A and B) at C4 level or above and assisted ventilatory function. Other exclusion criteria are the presence of decubitus, severe spasticity or musculoskeletal problems considered at risk of aggravation during testing or preventing completion of the test.

Recruitment of participants:

All newly injured patients who are admitted for rehabilitation at CSCI during the project period are included in the intervention (subproject 2) as it becomes a part of usual care during the project period. The Ph.D student is informed about new and future admissions at CSCI by local patient lists every week, and LTPAQ-SCI, ESES, QoL_SCI and NORMON is handed out to the patient and collected again by the Ph.D student. Date and time for the VO₂peak test is handed to the patients physiotherapist, who will make sure to enter it into the patients weekly schedule. The same procedure is repeated at discharge except that QoL_SCI is collected as a part of existing procedures and PHQ-2 is collected by the Ph.D student. In subproject 1, data for VO₂peak at CSCI will only be collected at discharge. All newly injured patients who are admitted for rehabilitation at VCR in the same period are recruited for subproject 1 and data for BMI, SCIM III and ISNCSCI is collected as a part of existing procedures in usual care.

The coordination related to booking of the DEXA-scan and transportation for this is managed by the secretaries. Ordination of the DEXA-scan as well as blood samples related to metabolic profile is handled by the doctors.

Ethical considerations

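### The historic-control reading of VO₂peak must rest on discharge values from non-randomised cohorts, yet the plan names no between-cohort analysis and gives admission injury severity no role in adjustment

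*Protocol*

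**What the plan says.** - **Role of the control cohort.** The description of Sub project 1 states: "Data from this subproject serves as a historic control in the Ph.D project". The Purpose section says the same of the BMI survey.
- **Who enters.** Under Participants, inclusion- and exclusion criteria, patients injured within the previous 12 months are taken "regardless of age, neurological level of lesion and completeness of the injury".
- **Severity at admission, controls.** Under Sub project 1, "data concerning BMI, level of functioning (SCIM III) and neurological status (ISNCSCI) are collected at admission and discharge".
- **Severity at admission, programme patients.** Under Outcome measures, "All outcome measures will be collected at admission, discharge and follow-up 6 months after discharge". Neurological status and SCIM III are described there, among the secondary outcomes. Neither is named as a covariate, a stratification factor or a baseline characteristic.
- **VO₂peak in controls.** Under Recruitment of participants, in sub project 1 "data for VO₂peak at CSCI will only be collected at discharge". The Sub project 1 description also places the test at discharge. These specific statements take precedence over the general sentence that every outcome is measured at all three times.
- **Analysis.** The Statistics section gives descriptive summaries, "Changes over time is reported on the basis of paired t-test", and reliability statistics for sub projects 3 and 4. It names no between-cohort comparison.
- **Size.** "Patients will be included during a time period of 18 corresponding to approximately 40 – 60 patients" (the 18 has no unit). Sub project 1 expects 100 patients over two centres in 9 months; the share from CSCI, the only centre with control VO₂peak, is not given.

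**The concern.** A paired test compares each patient with himself or herself and says nothing about the programme against usual rehabilitation. Patients in primary rehabilitation are expected to gain fitness anyway; the Background section cites a 24% rise in VO₂peak during early rehabilitation. The historic control is there to separate that recovery from a programme effect.

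For VO₂peak the control cohort has no admission value. Change cannot be compared and baseline fitness cannot be balanced, so what remains is a contrast of discharge values between two cohorts recruited one after the other. The protocol itself treats severity as relevant to this outcome: level and completeness decide who is excluded from the test, workload steps depend on the level of lesion, and the programme components a patient receives depend on the level of injury. If the cohorts differ systematically in case mix, an unadjusted contrast credits that difference to the programme.

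**Working it through.** The protocol gives no power calculation, effect size or SD, so there is no figure to reproduce. Results are in SD units of the outcome, with an assumed two-sided 5% level and, where used, 80% power.

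**1. Cohort sizes.** Programme: 40–60 (Statistics). Reading the 18 as months and scaling to the 9-month control window gives 40 × 9/18 = 20 to 60 × 9/18 = 30 CSCI controls. Sub project 2 expects 50–60 complete data sets in 12–18 months including follow-up, which implies a faster intake, and 20–30 from CSCI would leave 70–80 of the 100 controls to the other centre. I therefore carry an assumed range of about 20–60.

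**2. Chance imbalance.** For a severity factor present in half of patients (assumed), SE of the difference in shares = √(0.25/n₁ + 0.25/n₂). SE of the unadjusted contrast = √(1/n₁ + 1/n₂).

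| Controls, programme | SE of share difference | SE of contrast (SD) |
|---|---|---|
| 20, 40 | 0.137 | 0.274 |
| 30, 60 | 0.112 | 0.224 |
| 50, 50 | 0.100 | 0.200 |

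At 25 and 50 patients the SE of the share difference is 0.122, so with an assumed 1 SD outcome gap between severity groups a one-SE imbalance moves the contrast by about 0.12 SD. This variation is already inside the contrast's own SE of 0.245 SD. It is lost precision, not bias.

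**3. Precision gained by adjustment.** With gap D, R² = 0.25 × D², and the gain in effective patients is 1/(1 − R²) − 1.
- D = 0.5: R² = 0.0625, gain 7%.
- D = 1.0: R² = 0.25, gain 33%.
- D = 1.5: R² = 0.5625, gain 129%.

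These are before degrees of freedom. With three covariate terms and 60 patients, multiplying by (N − 3 − k)/(N − 3) = 54/57 leaves 1.067 × 0.947 = 1.01 at D = 0.5 and 1.333 × 0.947 = 1.26 at D = 1.

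**4. Systematic imbalance.** Bias b = difference in shares × D. A 20-point difference with D = 1 gives b = 0.20. False-positive rate = 1 − Φ(1.96 − b/SE) + Φ(−1.96 − b/SE).
- 50 and 50, b = 0.20: b/SE = 1.0, so 1 − Φ(0.96) + Φ(−2.96) = 17%. For b = 0.10 it is 7.9%; for b = 0.30, 32%.
- 20 controls and 40 programme patients, b = 0.20: b/SE = 0.730, rate 11%.
- 60 and 60, b = 0.20: b/SE = 1.095, rate 19.5%.

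An unadjusted interval does not cover this error, and a larger cohort makes the false-positive rate worse.

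**5. Price if severity explained nothing.** The detectable difference is multiplied by √((N − 3)/(N − 3 − k)).
- 50 and 50: √(97/92) = 1.027 for k = 5, √(97/89) = 1.044 for k = 8.
- 30 controls and 40 programme patients: √(67/62) = 1.039 for k = 5, √(67/59) = 1.066 for k = 8.

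That is about 3–7%. A shorter covariate list costs less: at 20 and 40 patients with k = 3, √(57/54) = 1.027.

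**The case against.** **The cited test is a within-patient analysis suited to a pre-post study, and covariates belong in an analysis plan that is not shown.** Half of this stands. The paired test is not in itself a wrong method for change, and a reader might infer that the protocol prescribes an unadjusted comparison of the cohorts. It does not: no such comparison is stated, adjusted or not. But the protocol names a historic control and fixes as its only inference on change a method that cannot use that control for VO₂peak. That goes beyond detail left for later.

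**The chance shift is already in the standard error.** This stands. For chance imbalance the benefit is precision alone, and it is small if the severity gap is only 0.5 SD.

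**Severity adjustment would settle case mix at no cost.** A reader might infer this because the data are already collected. It does not follow. Only measured and correctly modelled differences are reduced; calendar change, unmeasured factors and selective completion of the test remain, and there is a price in degrees of freedom.

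**Imbalance could equal a real programme effect.** This too is tempting, but the protocol gives neither an expected effect nor an SD for VO₂peak, so it cannot be said.

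**Case mix is narrower for VO₂peak.** True in part: motor-complete injury at C4 or above and assisted ventilation are excluded from the test. Wide variation in level, completeness and age remains.

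**Conclusion.** The point holds in a limited form and should be acted on. As written, the plan leaves the historic-control reading of VO₂peak as an unadjusted contrast of discharge values, although usable admission severity data exist in both cohorts. The exposure is to systematic case-mix difference; no such difference is shown to exist, since the documents give no case-mix figures. The false-positive rates above rest on the assumed 20-point imbalance, 1 SD gap and cohort sizes, and the precision gains on an assumed gap of 0.5–1.5 SD and a factor present in half of patients. The CSCI control number is also an assumption. The direction of the conclusion does not depend on these values; its size does.

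**What to change.** Amend the Statistics section to do the following.

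- State that CSCI controls and programme patients are compared by a linear model with a term for cohort. Restricting this to CSCI keeps centre from being mixed with cohort, because the other centre supplies only BMI, SCIM III and ISNCSCI.
- Prespecify a short set of admission covariates: an AIS grouping, tetraplegia or paraplegia, age, and the admission value of the outcome where both cohorts have it (not available for VO₂peak). Time from injury to admission is optional.
- Use admission severity, never discharge ISNCSCI or SCIM III, which the programme could affect.
- Leave out a term for calendar period: controls precede the programme, so it would be nearly aliased with cohort.
- Report admission ISNCSCI and SCIM III by cohort as baseline characteristics.
- State as limitations that calendar change, unmeasured differences and selective testing are not dealt with by this model.

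The paired t-test can stay as the description of within-cohort change. The cost is wording only; the data are already planned, and the statistical price is the small loss of degrees of freedom shown above.

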Sub project 2. A systematic interdisciplinary multimodal intervention which, as a part of usual care, facilitates PA, healthy diet and maintenance after discharge through strategic patient education, with the aim of decreasing cardiovascular risk factors.

This pre- post study includes all patients with a new SCI who are admitted at CSCI during a period of 12- 18 months including follow up. Complete data sets from admission to follow up is expected for approximately 50-60 patients during this period. The multimodal, interdisciplinary, patient activating and patient supportive intervention will be a part of usual care during the project period, and all newly injured patients will receive all the multimodal components, or parts of them, dependent on eg. the level of injury. Rehabilitation of the physical level of functioning and physical capacity will take place unchanged as usual.

A central part of the intervention is to create a uniform and systematic approach when the patients receive information and instructions about cardiovascular risk factors, PA and a healthy diet through targeted strategic patient education, which includes targeted, individualized and systematic, face- to-face interaction between patients and health care professionals, while working towards, and improving a specific health related outcome through adherence to the working processes, medicine and lifestyle. The concept has been used previously for patient education and prophylaxis of catheter related sepsis [44]. Strategic patient education is carried out by all the health care professions in different settings with a focus on clarifying the importance of PA and a healthy diet. This will take place during the individual functional training and rehabilitation in general, and in conjunction with feedback about outcome measures and tests with subsequent instructions. Strategic patient education will also be integrated as a concept in the education of the interdisciplinary health care professionals and mentors with a SCI, as they will be implementing the content of the education into a daily clinical setting.

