A significant challenge to the project, and a factor able to impact on the projects completion is the logistic planning related to the patients having the necessary tests made at the right times at admission, discharge and follow up, for which they need to be called in for.

Some of the data used in project and many of the settings and work flows used in the intervention is a part of the existing settings and procedures, which is ensuring the completion of the project.

At Clinic for Spinal Cord Injuries the clinic management by head nurse [name], leading therapist [name] and head of the clinic [name] are responsible for ensuring the setting necessary for completing the project and its elements. At an overall level center manager nurse [name], Neuroscience centre, Rigshospitalet is responsible for ensuring the necessary setting for the completion of the project.

Changes to the protocol will be described in an additional protocol.

Publication of results:

Attempts will be made to publish the projects results in relevant scientific journal such as BMJ Open, Archives of Physical Rehabilitation Medicine, Journal of Spinal Cord Medicine and Spinal Cord. Listed below are the preliminary titles of the articles.

The Ph.D student will be primary author on all articles primary supervisor [name] will be last author on articles related to subproject 2, 3 and 4, while co- supervisors [name] and [name] are last authors on articles related to subproject 1 and the protocol article respectively. Clinical nurse specialist [name] is co- author on the protocol article and the article related to subproject 1

Protocol article: Health and Cardiovascular Risk Reduction in People with Spinal Cord Injury - Physical Activity, Healthy Diet and Adherence after Discharge from Primary Rehabilitation.

1. Longitudinal National Survey of Body Mass Index and Measures of Functional Recovery, Depression, Quality of life, Physical Activity and Exercise Self Efficacy during Inpatient Spinal Cord Injury Rehabilitation and Follow Up.
2. Effects of a Systematic and Interdisciplinary, Multimodal and Patient Engaging Intervention on , Metabolic Markers, Body Composition, Physical Activity and Diet, Quality of Life and Exercise Self Efficacy during Inpatient Rehabilitation with Follow up, Facilitating Adaptation to Physical Activity and Healthy Diet in People with Spinal Cord Injury.

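### Change over three visits is to be analysed only by paired t-tests, which drop incomplete pairs and are biased when missingness depends on earlier results; an unstructured repeated-measures model is the better primary analysis, within limits

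*Protocol*

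**What the plan says.** The Outcome measures section sets three visits: "All outcome measures will be collected at admission, discharge and follow-up 6 months after discharge". Recruitment of participants makes one exception for the primary outcome: "In subproject 1, data for VO₂peak at CSCI will only be collected at discharge".

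For analysis, the Statistics section is descriptive ("Numeric continuous data collected at admission, discharge and follow up is reported descriptively as mean and standard deviation", or medians and quartiles) apart from one sentence on change: "Changes over time is reported on the basis of paired t-test". It names no other method for change and does not mention patients with one value of a pair missing.

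Three places bear on completeness:
- Risk assessment and changes to the protocol names as a serious threat the "logistic planning related to the patients having the necessary tests made at the right times at admission, discharge and follow up". It also allows that staff may fail to collect necessary data.
- The exclusion criteria rule out VO₂peak testing for "the presence of decubitus, severe spasticity or musculoskeletal problems considered at risk of aggravation during testing", among other conditions.
- On numbers, the Statistics section says "Patients will be included during a time period of 18 corresponding to approximately 40 – 60 patients", while Sub project 2 says "Complete data sets from admission to follow up is expected for approximately 50-60 patients".

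**The concern.** A paired test of two visits keeps only patients measured at both and ignores the third. Its estimate describes the whole cohort only if being incomplete is unrelated to the change. If patients who gained little in rehabilitation return less often, those with follow-up values are selected for a large earlier gain. Part of that gain is chance and is given back at the next measurement. The paired test can then show a decline after discharge where there is none, and overstate the total gain since admission.

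Maintenance after discharge is the project's stated hypothesis, and the discharge-to-follow-up contrast is the one most exposed to loss at follow-up. With 40-60 patients, partial records are also too valuable to discard.

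**Working it through.** The protocol gives no power calculation, attrition rate, SD or correlation, so it has no figure of its own to reproduce. From the documents come the three visits, the paired t-test and 40-60 included patients. Everything else below is assumed: SD 1 at each visit, jointly normal outcomes, and correlations written as r12/r23/r13 (admission-discharge, discharge-follow-up, admission-follow-up).

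**1. Pairs kept.** If 15% miss each visit independently, the fraction with both values is 0.85² = 0.7225. Of 40-60 included, 40 × 0.7225 = 28.9 and 60 × 0.7225 = 43.4, so about 29-43. The standard error of a paired contrast rises by 1/0.85 = 1.18 against complete data.

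**2. Bias when follow-up loss depends on the earlier gain.** Let G be the admission-to-discharge gain, and let the shift be the mean G of retained patients minus the mean G of all. Then

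bias = shift × Cov(change, G) / Var(G), with Var(G) = 2(1 − r12).

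Cov is r23 − r13 − 1 + r12 for discharge to follow-up and r23 − r13 − r12 + 1 for admission to follow-up.

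| r12/r23/r13 | Factor, discharge to follow-up | Factor, admission to follow-up |
|---|---|---|
| 0.7/0.7/0.7 | −0.30/0.60 = −0.50 | 0.30/0.60 = 0.50 |
| 0.8/0.8/0.65 | −0.05/0.40 = −0.125 | 0.35/0.40 = 0.875 |
| 0.6/0.9/0.55 | −0.05/0.80 = −0.0625 | 0.75/0.80 = 0.9375 |

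Simulation with 55 patients, true means 0/0.5/0.5 SD and 32% missing follow-up agrees:
- Equal correlations of 0.7: the paired estimate is −0.14 SD for discharge to follow-up (true 0) and 0.63 for admission to follow-up (true 0.50, bias +0.13). The unstructured model gives 0.00 and 0.50.
- Unequal correlations: the discharge-to-follow-up bias shrinks to about −0.02 to −0.03, while the admission-to-follow-up bias grows to as much as +0.33. The latter implies a shift of 0.33/0.9375 = 0.35, and 0.35 × −0.0625 = −0.02, as simulated.
- 15% loss with correlation 0.7: −0.03 to −0.08 SD for discharge to follow-up, against a standard error of about 0.11. Under unequal correlations it is about −0.01.

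**3. Bias when follow-up loss depends on a single earlier value** (50 patients, low values more often missing, correlations 0.6/0.6/0.5 and 0.8/0.8/0.7).
- Loss depends on the discharge value: discharge to follow-up is biased by −0.05 to −0.10 SD at 20% loss and −0.09 to −0.17 at 40%. Admission to follow-up is about unbiased (−0.012 to +0.011).
- Loss depends on the admission value: admission to follow-up is biased by −0.07 to −0.20 SD over 20-40% loss, so the sign depends on the mechanism.
- The unstructured model stays within about 0.013 SD of zero throughout.

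**4. Where the model does not help: missingness depends on the current value.**
- Follow-up missing because of its own low value (32%, correlation 0.7): discharge to follow-up (true 0) is +0.11 paired and +0.18 with the model. Admission to follow-up (true 0.50) is 0.61 and 0.67.
- Admission missing because of its own low value (20-40%): changes from admission are biased by −0.05 to −0.22 SD paired and −0.09 to −0.30 with the model.

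**5. Covariance structure.** Under gain-dependent loss (32%), discharge-to-follow-up estimates (true 0) were:

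| r12/r23/r13 | Paired | Random intercept | Unstructured |
|---|---|---|---|
| 0.8/0.8/0.65 | −0.03 | +0.07 | 0.00 |
| 0.6/0.9/0.55 | −0.03 | +0.15 | −0.01 |

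A random intercept alone is worse here than the method it would replace.

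**The case against.** The strongest objection is that the protocol's own reason for health-linked gaps is inability to perform the exercise test. That concerns the patient's state at the visit, not an earlier result, and step 4 shows that the model can then be further off. This stands. A reader might infer that a mixed model cures the missing-data problem; nothing in the protocol supports that.

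Second, a reader might infer that the protocol itself shows missingness to be related to health. It does not. The risk section speaks of logistics and says that existing routines help secure completion. The exclusion criteria do not say that testability is reassessed at each visit. Body weight, SCIM III and the questionnaires do not need an exercise test. Incomplete visits are foreseeable; their cause is open.

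Third, the 50-60 in Sub project 2 are described as complete data sets already, so discounting them for missed visits would count the loss twice. The 40-60 included are the right base.

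Fourth, a paired t-test is conventional in a small pragmatic pre-post study, and missing-data handling is often left to an analysis plan. That excuses the protocol's silence on incomplete pairs, but not its choice of method, which it fixes. With complete data the unstructured model returns the same mean changes, so naming it costs nothing in that case.

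**Conclusion.** The point holds in limited form. The protocol commits to a method for change that drops incomplete pairs and is biased when missingness depends on earlier observed results. Under assumed follow-up loss of 15-32%, depending on the gain or the discharge value, the bias is roughly −0.01 to −0.14 SD for discharge to follow-up and about 0 to +0.33 SD for admission to follow-up. Heavier loss, or dependence on the admission value, changes the size and can reverse the sign of the latter. At low loss the bias is below one standard error.

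The protocol does not show that its results will be biased, or by how much. Nor does it support a claim about change in VO₂peak in subproject 1: with a discharge measurement only, there is no change to estimate by either method. Patients who are never tested inform neither analysis.

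**What to change.** In the Statistics section, for each continuous outcome measured repeatedly:
- Make the primary analysis of change a likelihood-based repeated-measures model with visit as a categorical effect and unstructured covariance (not a random intercept alone), using every patient with at least one value.
- Report discharge minus admission, follow-up minus discharge and follow-up minus admission, each with a 95% CI.
- Keep the paired t-test as a complete-pair sensitivity analysis.
- State that the model assumes missingness is explained by observed visits. Add a sensitivity analysis for patients untestable because of their state at that visit, for example by shifting their unobserved values over a stated range, and record the reason for each missing test.
- State that this does not apply to VO₂peak in subproject 1.

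The cost is a few sentences and modest extra analysis, with no new patients, visits or measurements. The downside to declare is the one in step 4: under missingness on the current value the model may be further from the truth than the paired test, so the two should be reported side by side.
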